### 2. Rationale of the Project:

Breast cancer is the most commonly diagnosed cancer among women and remains a leading cause of cancer-related mortality. Globally, it ranks second only to lung cancer in incidence, with both accounting for approximately 11.6% of all diagnosed cancer cases (1). In the United States, the lifetime risk for a woman to develop breast cancer is estimated at 13%, indicating that one in eight women will be affected during their lifetime (2).

Over the past two decades, significant advances in breast cancer research have markedly improved our understanding of the disease, enabling the development of more effective and less toxic treatments. Enhanced public awareness and improved screening methods have facilitated early detection at stages amenable to surgical resection and curative therapy. Consequently, survival rates—especially among younger women—have substantially improved (3).

Surgical treatment of breast cancer includes both conservative and non-conservative approaches. Conservative surgeries account for approximately 40% of all procedures, with quadrantectomy being the most commonly performed among them (4). However, surgical treatment may lead to various complications, including chronic postoperative pain (5).

Post-mastectomy pain syndrome (PMPS) is typically defined as chronic pain in the breast or chest wall persisting for at least three months following cancer treatment. It arises after surgical interventions for breast cancer and is believed to result from primary nerve injury or dysfunction of the nervous system (6,7). Clinically, it presents with features of neuropathic pain such as burning, tingling, stabbing, or shooting sensations, and hyperesthesia (8). Although no standardized diagnostic criteria exist, the estimated incidence ranges from 40% to 50% (7,9), with about half of affected women reporting moderate to severe pain (10).

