Younger age (<40 years) has been identified as a major risk factor, though age does not appear to correlate with the intensity of reported pain (10). Severe acute postoperative pain is also considered a predictive factor for the development of chronic pain. Furthermore, radiotherapy to the breast and/or axillary region has been associated with an increased risk of chronic pain when compared to patients who did not receive radiation therapy (11). Among surgical contributors to PMPS, extensive axillary lymph node dissection is significant due to the increased risk of intercostobrachial nerve injury, which may lead to neuropathic pain (12,13).

Strategies aimed at reducing the risk of PMPS emphasize optimizing perioperative pain management. Techniques such as paravertebral, erector spinae plane (ESP), and pectoral

nerve blocks are routinely applied in appropriate surgical cases to reduce postoperative pain and minimize the risk of chronic pain development in many centers, including ours (14). Both ESP and PECS I-II blocks have demonstrated efficacy and are associated with low complication rates (14,15,16).

In our study, we aim to observe the incidence of chronic pain following mastectomy in patients who have received either a pectoral nerve block (PECS I-II) or an erector spinae plane (ESP) block as part of their pain management strategy. These blocks will be administered by the attending anesthesiologist after general anesthesia induction and prior to the initiation of surgery. The choice and timing of the block will be determined independently by the anesthesiologist and not influenced by the study team. The primary outcome of this study is to compare the incidence of chronic postoperative pain between the two groups. The secondary outcome is to assess the impact of these blocks on acute postoperative pain levels and opioid requirements.

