#### **3.3 Study Population, Sample Size, and Study Groups**

Following approval by the Hacettepe University Ethical Committee, patients aged 18 to 65 years, classified as ASA physical status I-II, and scheduled to undergo elective modified radical mastectomy or simple mastectomy with sentinel/axillary lymph node dissection under general anesthesia at Hacettepe University Hospitals between April 15 and May 15, 2024, will be included. Patients must have already been scheduled to receive either an ESP or PECS I-II block for postoperative pain management independently of the study. A total of 40 patients will be enrolled, with 20 in each group at least. Patients with coagulation disorders, allergies to local anesthetics, obesity ( $BMI > 35 \text{ kg/m}^2$ ), infection at the injection site, pre-existing neurological deficits, or unwillingness to participate, as well as those with failed blocks, will be excluded. The decision to perform blocks is made by the responsible anesthesiologist and will not be influenced by the study team.

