#### **3.5. Research Method and Data Collection Tools:**

Upon admission to the operating room, non-invasive arterial blood pressure, electrocardiogram, and peripheral oxygen saturation monitoring will be conducted before

the induction of general anesthesia. This is the routine monitoring protocol applied prior to anesthesia. All patients will receive standard general anesthesia and standard ventilation modes. The research team will not intervene in the anesthesia procedure.

According to the standard anesthesia practice in these cases, anesthesia induction is performed with propofol (1.5–2.5 mg/kg), rocuronium (0.4–0.6 mg/kg), and fentanyl (1–2 mcg/kg), with a 50% oxygen-air mixture. Standard ventilator settings are applied.

Anesthesia maintenance consists of 2% sevoflurane with 50% oxygen-air mixture. These practices are routine in our operating theater and are not specifically designed for this study. In the event of any non-routine requirement, decisions will be made by the responsible anesthesiologist, without any intervention from the research team. The study will commence after anesthesia induction and block application.

Following the induction of general anesthesia, the responsible anesthesiologist will independently administer either the PECS I-II or ESP block prior to surgical incision. The choice of block will not be influenced by the study and will be determined solely by the anesthesiologist, regardless of group distribution. The research team will not interfere in the selection or method of block administration.

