#### Postoperative Pain Control:

In addition to routine 3×1000 mg IV paracetamol, rescue analgesia with IV tramadol (0.5 mg/kg) will be administered as needed. These practices are part of our standard multimodal analgesia protocol and not specific to the study. After discharge, patients will be transitioned to oral paracetamol, with a recommendation of 3×500 mg daily for one month if necessary

Postoperative follow-up interviews will be conducted by a study assistant. Time of initial pain, and whether rescue analgesia was needed within the first 24 hours, will be recorded. Pain levels will be assessed at 20 minutes, 6 hours, and 1 day postoperatively using the Numerical Rating Scale (NRS). If NRS >0, the DN4 (Douleur Neuropathique 4) questionnaire will be administered. At the 3-month follow-up, patients will be contacted via phone and evaluated with the DN2 and SF-12 questionnaires. No blood samples or invasive procedures will be performed for research purposes.

The NRS is a simple and widely used 0–10 scale to assess pain severity, from "0 = no pain" to "10 = worst imaginable pain." It is considered valid and reliable. The DN4 questionnaire, administered by clinicians, includes 10 items to evaluate neuropathic pain, with a sensitivity of 83% and specificity of 90%. A score ≥4 indicates neuropathic pain. The SF-12 Quality of Life questionnaire, validated in Turkish, consists of 12 items and is used to assess overall health status and quality of life.

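### The primary outcome is an incidence of chronic pain, but no pain assessment is scheduled before surgery, so persisting prior pain cannot be reliably told from new pain or checked for balance between the groups

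*Combined protocol and SAP*

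**What the plan says.** Section 2 (Rationale of the Project) sets the outcome: "The primary outcome of this study is to compare the incidence of chronic postoperative pain between the two groups". It describes the syndrome as "chronic pain in the breast or chest wall persisting for at least three months following cancer treatment" and says that it arises after breast cancer surgery. New onset is thus part of the concept.

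The measurements are all postoperative:

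- Section 3.5 (Research Method and Data Collection Tools): "The study will commence after anesthesia induction and block application".
- Postoperative Pain Control: "Pain levels will be assessed at 20 minutes, 6 hours, and 1 day postoperatively using the Numerical Rating Scale (NRS". DN4 is added when the NRS is above zero.
- Same section: "At the 3-month follow-up, patients will be contacted via phone and evaluated with the DN2 and SF-12 questionnaires". No question on onset or on pain before surgery is described, and no rule says which 3-month answers make a patient a case.

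Regional pain is not among the exclusions in section 3.3. The nearest wording is in "infection at the injection site, pre-existing neurological deficits, or unwillingness to participate". Section 3.6 lists the patient data as demographics, body size, ASA score, comorbidities and intraoperative details. It has no pain item.

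The groups are not randomised: "The choice of block will not be influenced by the study and will be determined solely by the anesthesiologist, regardless of group distribution". Section 3.7 compares categorical outcomes by chi-square or Fisher's exact test, with no covariate or stratification.

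**The concern.** An incidence counts new cases among people who did not have the condition at the start. This plan has no dependable way to identify those people. A patient with breast, chest wall or arm pain before surgery that is still there at 3 months could be counted as a case of chronic postoperative pain, depending on a case rule that is not yet written.

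Two consequences follow. If prior pain is equally common in both groups, it raises both 3-month proportions or lowers them, depending on how often it persists, and it dilutes a true difference. If it is unequal, it can create or hide a difference. The block is chosen by the anesthesiologist, so balance cannot be assumed, and without a baseline record it cannot be checked or allowed for.

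**Working it through.** **No figure in the plan to reproduce.** Section 3.3 gives 40 patients, at least 20 per group, without a target difference, power or dropout rate. The point is about measurement and does not depend on a stated calculation. The arithmetic below only illustrates possible size.

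**Inputs from the protocol.** 20 per group (section 3.3). Background incidence of 40% to 50% (section 2); the midpoint of 45% is used as the new-onset rate.

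**Inputs assumed, not in the documents.** q is the share of a group with regional pain before surgery. s is the share of those patients whose pain persists and is counted at 3 months.

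**Model.** With I the new-onset incidence among patients without prior pain, the apparent 3-month proportion is m = (1 − q)·I + q·s.

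**Step 1: unequal prior pain, no block effect.** The spurious gap is (q₂ − q₁)·(s − I). With q of 10% versus 30% and I = 45%:

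| Persistence s | m at q = 10% | m at q = 30% | Spurious gap |
|---|---|---|---|
| 100% | 0.405 + 0.100 = 50.5% | 0.315 + 0.300 = 61.5% | 11 points |
| 70% | 0.405 + 0.070 = 47.5% | 0.315 + 0.210 = 52.5% | 5 points |
| 50% | 0.405 + 0.050 = 45.5% | 0.315 + 0.150 = 46.5% | 1 point |
| 45% | 45% | 45% | 0 |

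Below 45% persistence, s − I is negative and the gap reverses. At full persistence the gap runs from 12 points (I = 40%) to 10 points (I = 50%).

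**Step 2: equal prior pain, real block effect.** With the same q and s in both groups, the observed difference is (1 − q) times the true one. A 20-point difference becomes 19 at q = 5%, 18 at 10%, 16 at 20% and 14 at 30%.

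**Step 3: scale against sampling error.** The standard error of the difference at 20 per group is √(2 × 0.45 × 0.55 / 20) = 0.157, or about 16 points. Every gap in Step 1 is smaller than this.

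**Step 4: effect on the test.** The exact two-sided Fisher rejection rate at 0.05, with 20 versus 20 and I = 45%, is 2.2% with no imbalance. It is 5.6% for q of 10% versus 30% at full persistence.

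**Step 5: imbalance by chance alone.** If both groups have the same underlying q, they differ by 3 or more affected patients with probability 18% at q = 10%, 32% at 20% and 39% at 30%. Selection by the anesthesiologist could add to this.

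**The case against.** **Prior pain is partly covered.** Neurological deficits are excluded and comorbidities are recorded. The syndrome is described as neuropathic, and DN2 is the only pain tool named at 3 months. If cases are to be neuropathic, ordinary tumour or biopsy soreness need not count. This stands in part, and it would be wrong to infer that the plan captures nothing about prior pain. But a deficit is not pain, a comorbidity entry need not give site, intensity or duration, and without a case rule the overlap cannot be determined.

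**The baseline is not wholly lost after surgery.** A reader might infer that it is. Patients could still be asked at the 24-hour interview or the 3-month call, with recall error. This stands: the contemporaneous score is lost, but recalled information is possible.

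**The size is modest and rests on assumed inputs.** This stands. No preoperative pain rate is given, nothing links block choice to prior pain, and a threefold imbalance with full persistence is an upper-end case. Larger gaps also remain: the unwritten case rule and the unadjusted comparison of non-randomised groups.

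**Restricting the analysis to pain-free patients costs precision.** This also stands. It changes the population and shrinks a study of 20 per group, so it is better as a supporting analysis than as the main one.

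**Conclusion.** The concern holds. Followed exactly, the plan yields a 3-month proportion that can mix old and new pain, in non-randomised groups whose baseline pain is not scheduled to be measured and is not used in the analysis.

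Direction and size are unknown. Under the assumptions shown (45% new-onset incidence, prior pain 10% versus 30%), the spurious gap is anywhere from 11 points down to zero as persistence falls from 100% to 45%, and reversed below that, against a standard error of about 16 points. A reader might infer that the comparison is biased towards one block, or that false-positive results become common. The documents support neither: they do not tie prior pain to block choice, and even the extreme case moves Fisher's rejection rate only from 2.2% to 5.6%. The harm is an estimate whose bias cannot be examined.

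This should be corrected because it is cheap to do and a contemporaneous baseline can be obtained only before surgery.

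**What to change.** **Sections 3.5 and 3.6.** Have the study assistant record before surgery, on the operated side, a 0–10 NRS for breast/chest wall and a separate one for axilla/arm, and whether pain in either place has lasted at least 3 months. The second region is needed because section 2 notes that "extensive axillary lymph node dissection is significant due to the increased risk of intercostobrachial nerve injury". Amend the sentence in 3.5 on when the study starts. Ask the same regional NRS question at the 3-month call, alongside DN2 and SF-12. The 3-month case rule must be written in any event.

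**Section 3.7.** Show baseline regional pain by group. Report 3-month pain in all patients, stratified by baseline regional pain (yes/no; yes if either preoperative NRS is above 0 or pain there has lasted at least 3 months). Report incidence among patients without baseline regional pain as a supporting analysis, and state its smaller numbers.

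**Patients already operated on.** Ask about prior pain at the 24-hour interview or the 3-month call and flag the answer as recalled. If no baseline is obtained, call the outcome the 3-month prevalence of pain.

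**Cost.** A few minutes per patient, one more telephone question and a protocol/ethics amendment; no new procedure. The strata are small: at 10% to 30% prior pain, 2 to 6 of 20 patients per group fall in the prior-pain stratum. The pain-free subset loses precision: with 18 versus 14 patients the standard error is √(0.2475/18 + 0.2475/14) = 0.177, about 18 points, and more if mild preoperative soreness is common. Other confounding by block choice remains.

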#### **3.2 Study Timeline**

April 15, 2024 – August 15, 2024.

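### The primary outcome, incidence of chronic postoperative pain, is not operationally defined: the 3-month call has no specified pain item and the plan gives no case rule

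*Combined protocol and SAP*

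**What the plan says.** Section 2 (Rationale of the Project) sets the endpoint: "The primary outcome of this study is to compare the incidence of chronic postoperative pain between the two groups". As background, the same section describes post-mastectomy pain syndrome, which "is typically defined as chronic pain in the breast or chest wall persisting for at least three months following cancer treatment". It adds that the syndrome presents with neuropathic features and that there are no standardized criteria for diagnosing it.

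Section 3.5 (Postoperative Pain Control) schedules the NRS at 20 minutes, 6 hours and 1 day, and a score above 0 leads to the DN4. For the later follow-up it says: "At the 3-month follow-up, patients will be contacted via phone and evaluated with the DN2 and SF-12 questionnaires". Section 3.6 names the same two instruments for 3 months.

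The DN4 is described as a 10-item tool, with a score of 4 or more indicating neuropathic pain. The SF-12 is described as a measure of general health and quality of life. The DN2 is not described anywhere. Section 3.7 assigns tests by type of data, with chi-square or Fisher's exact test for categorical variables. It names no primary variable.

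**The concern.** An incidence is the number of patients who meet a yes/no rule, divided by the number assessed. It needs a recorded item and a rule that turns the answer into case or non-case. For the primary outcome, the plan states neither.

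Three things are at stake:

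- **Collection.** Followed as written, no specified item records at 3 months whether pain is present or how intense it is. If callers ask in their own words, the question may differ between patients. Pain status that was not recorded then cannot be recovered by later analysis.
- **Choice after the fact.** With no DN2 scoring and no case rule fixed, either could be chosen once the data are visible.
- **Target.** If the DN2 is a neuropathic screen (the documents do not say), using it as the case rule would miss chronic pain that is not neuropathic. The stated outcome is not limited to neuropathic pain.

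**Working it through.** There is no plan figure to reproduce. The total of 40 is given without power, expected rates or dropout, and this point does not depend on it. The check sets what the primary outcome needs against what the text supplies.

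| Needed to count a case | What the plan supplies | Status |
|---|---|---|
| Concept | Chronic postoperative pain (section 2) | Stated |
| Time point | 3-month call (3.5, 3.6); three months in the background description (section 2) | Can be inferred |
| Item for presence of pain | NRS at 20 minutes, 6 hours, 1 day; 0 of 3 assessments at 3 months | Missing |
| Item for intensity | As above | Missing |
| Site of pain | Breast or chest wall, in the background description only | Not adopted for the endpoint |
| Pain before surgery | The patient data listed in 3.6 include comorbidities but no pain item | Missing |
| Case rule | DN4 score of 4 or more, for neuropathic pain | Missing for DN2 and for chronic pain |
| Test | Chi-square or Fisher's exact test (3.7) | Can be inferred |

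**Can the DN4 cut-off be carried over?** Not on the text given. It is stated for a 10-item questionnaire. The number of DN2 items and their scoring are not stated, so a score of 4 has no known meaning on the DN2. Neither of the 2 instruments used at 3 months has a stated rule for chronic pain.

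**Does the background description serve as the rule?** It gives a site and a duration but no question, instrument or threshold. Its duration element is also open. If pain begins t months after surgery, its duration at a 3-month call is 3 − t, which is below 3 for every t above 0. Counting pain that is present at 3 months and counting pain that has lasted three months therefore classify such a patient differently. The plan does not choose between them.

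**Is there room to repair it later?** Enrolment is "between April 15 and May 15, 2024, will be included". Adding 3 months: April 15 becomes July 15 and May 15 becomes August 15, 2024. The timeline in section 3.2 is "April 15, 2024 – August 15, 2024", so the last calls fall on its final day. The items have to be in the call itself.

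**Could the choice of rule matter once intensity is recorded?** This is an illustration only. Section 2 says "the estimated incidence ranges from 40% to 50% (7,9), with about half of affected women reporting moderate to severe pain", and section 3.3 says "A total of 40 patients will be enrolled, with 20 in each group at least". Assume that these rates apply here, that 40–50% can be read as any chronic pain, and that all 20 per group are reached:

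- Any pain: 0.40 × 20 = 8 to 0.50 × 20 = 10 cases per group.
- Moderate to severe: 0.5 × 0.40 = 0.20 and 0.5 × 0.50 = 0.25, so 0.20 × 20 = 4 to 0.25 × 20 = 5 cases per group.

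The two rates come from different cited sources (references 7 and 9 for the first, 10 for the second), so the product is rough. It shows only that the rule is not a formality.

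**The case against.** The best defence is that the reader can reconstruct the endpoint. Section 2 describes the syndrome, the call is at 3 months, and section 3.7 has a test for proportions. Because section 2 ties the syndrome to nerve injury and neuropathic features, a DN2-based endpoint would fit the protocol's rationale. A caller would also probably ask about pain.

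Part of this stands. A reader might infer that the outcome is not defined at all, but the concept is stated, and the time point and test can be inferred. What is missing is the operational definition. A reader might also infer that the call cannot identify pain. The documents do not show that either, because the content of the DN2 is not given. The proven gap is that no pain item or rule is specified. The defence does not fill it: the description is background, the DN2 is not named as the endpoint, and the caller's question is not written down.

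Three further inferences go too far:

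- **That the open rule halves or doubles the primary result.** Choosing between any pain and moderate-to-severe pain requires an intensity measure, which the written call does not specify. The choice open as written is the DN2 scoring or cut-off, and the documents give no figures for that.
- **That the choice of rule can be sized by which case counts reach significance.** Such thresholds mainly reflect 20 per group, and they change with the test, since section 3.7 allows either chi-square or Fisher's exact test.
- **That persistence can be ignored because radiotherapy pain starts late.** Section 2 says only that "radiotherapy to the breast and/or axillary region has been associated with an increased risk of chronic pain"; it says nothing about onset.

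**Conclusion.** The concern holds and needs fixing before the calls are made. The primary outcome has no operational definition, and this affects all 40 planned patients: 0 of 3 NRS assessments fall at 3 months, 0 of 2 instruments at 3 months have a stated chronic-pain rule, and the analysis section has no case definition. No numerical effect on the group comparison can be derived from the documents.

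The conclusion assumes that sections 3.5 and 3.6 list everything asked at 3 months; the two sections agree with each other. It does not depend on what the DN2 contains. The narrower warning, that non-neuropathic pain would be missed, applies only if the DN2 is a neuropathic screen.

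**What to change.** **If the calls are still to be made**

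- In 3.5 and 3.6, add to the 3-month call a question on pain at the operated breast or chest wall, including when it began and whether it was present before surgery, and an NRS 0–10 for that pain.
- In 3.5 and 3.7, fix one binary case rule before the first call and name it as the primary variable. An example is surgical-site pain with NRS above 0 at 3 months, the same threshold that already triggers the DN4. The rule must say how it treats the persistence element in section 2 and pain already present before surgery. Compare the groups by chi-square or Fisher's exact test.
- Report as secondary outcomes moderate-to-severe pain, with its NRS cut-off stated, and DN2, with its items and cut-off stated.

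**If the calls are complete**

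Rename the primary outcome to what was measured, state the DN2 items, fix the DN2 cut-off before any between-group comparison, and label the definition post hoc.

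**Cost**

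One to three extra questions in a call already planned, plus wording in 3.5, 3.6 and 3.7, with no extra visits or patients. A rule of NRS above 0 also counts mild pain, which is why moderate-to-severe pain should be reported alongside. The renaming route may give up the broader chronic-pain question, and the endpoint is then no longer pre-specified.
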